CKD-EPI	Chronic Kidney Disease Epidemiology Collaboration
CLIA	Clinical Laboratory Improvement Amendment of 1988
CRF	Case Report Form
CRIS	Clinical Research Information System
CRIMSON	Clinical Research Information Management System of the NIAID
DCR	Division of Clinical Research
DHHS	Department of Health and Human Services
DSMB	Data and Safety Monitoring Board
FDA	Food and Drug Administration
GCP	Good Clinical Practice
GFR	Glomerular Filtration Rate
HAC	Human Artificial Chromosome
hIgG	Human Polyclonal IgG
HIV	Human Immunodeficiency Virus
IB	Investigator's Brochure
ICF	Informed Consent Form
ICH	International Conference on Harmonization
IGIV	Immunoglobulin for Intravenous Use
IND	Investigational New Drug
IP	Intraperitoneal
IRB	Institutional Review Board
IV	Intravenous
K	Potassium
LDH	Lactate Dehydrogenase
MERS	Middle East Respiratory Syndrome
MERS-CoV	Middle East Respiratory Syndrome coronavirus
Na	Sodium
NIAID	National Institute of Allergy and Infectious Diseases
NIH	National Institutes of Health
OCRPRO	Office of Clinical Research Policy and Regulatory Operations
OHRP	Office for Human Research Protections
OTC	Over-the-Counter
PI	Principal Investigator
PK	Pharmacokinetics
RCHSPP	Regulatory Compliance and Human Subjects Protection Program
SAD	Single Ascending Dose
SAE	Serious Adverse Event/Serious Adverse Experience
SRCP	Safety Review and Communication Plan
SUSAR	Serious and Unexpected Suspected Adverse Reaction
Tc	Transchromosomal
TKO	Triple Knockout
UP	Unanticipated Problem
UPnonAE	Unanticipated Problem that is not an Adverse Event

PROTOCOL SUMMARY

Full Title: A Phase 1, Randomized Double-Blind, Placebo-Controlled, Single Ascending Dose Safety, Tolerability, and Pharmacokinetics Study of SAB-301 in Healthy Adults

Short Title: SAB-301

Clinical Phase: 1

IND Sponsor: OCRPRO/DCR/NIAID/NIH

Conducted by: LIR/NIAID/NIH

Principal Investigator: [name]

Sample Size: 38 subjects

Accrual Ceiling: 70 (up to 70 subjects screened to randomize a total of 38 subjects)

Study Population: Healthy Volunteers aged 18 to 60 years

Accrual Period: Start Date: April 2016
End Date: December 2016

Study Duration: Start Date: April 2016
End Date: April 2017

Study Design: Randomized, Double-Blind, Placebo-Controlled, Dose-escalating

Study Agent: Active: SAB-301
Control: Normal (0.9%) saline

Primary Objective: To evaluate the safety and tolerability of SAB-301 in healthy adults, following single intravenous administration at escalating dose-levels

Secondary Objectives:

- To evaluate the pharmacokinetics of intravenously administered SAB-301 in healthy adults, following single intravenous administration at escalating dose-levels
- To determine the ability of serum levels of SAB-301 to neutralize Middle East Respiratory Syndrome (MERS) virus
- To evaluate the immunogenicity of SAB-301

Primary Endpoint: Type and frequency of adverse events experienced by subjects receiving SAB-301 at escalating dose-levels, as compared to control saline

Secondary Endpoints:

- Pharmacokinetic profile of intravenously administered SAB-301 in healthy adults
- MERS virus neutralization assay
- Frequency and concentrations of antibodies caused by SAB-301, as measured by:
 - Anti-IgG antibodies using rheumatoid factor
 - Anti-SAB-301
 - Anti-Bovine Kappa light chain
 - Anti-██████████ Antibody

PRÉCIS

The administration of convalescent plasma or hyperimmune immunoglobulin is often used for treatment of emerging infectious diseases. However, production of large quantities of anti-pathogen human plasma and/or immunoglobulin with high affinity and avidity antibodies currently requires donations by convalescent humans, a process that can limit availability for a number of reasons. One novel alternative source is transchromosomal (Tc) cattle that produce fully human polyclonal IgG (hIgG) de novo and mount a robust antibody immune response after vaccination.

This study will evaluate the safety, tolerability, and immunogenicity of SAB-301, a fully human polyclonal anti-MERS IgG collected from transchromosomal cattle. Beginning with a low single-dose, subjects are randomized to receive either SAB-301 or a normal saline control, and evaluated on Study Days 1, 3, 7, 21, 42, and 90. The safety and tolerability is evaluated using symptoms, clinical laboratory tests, pharmacokinetics, and immunogenicity assays. Utilizing a series of stopping rules and a medical monitor, the dose will be escalated as safety and tolerability are established.

1 BACKGROUND INFORMATION AND SCIENTIFIC RATIONALE

1.1 Background

Middle East Respiratory Syndrome (MERS) currently has no available treatment. One option for treatment is the use of polyclonal antibodies. Human convalescent plasma and/or immunoglobulins (IGIV) have been used to effectively prevent and treat many viral infections. However, production of large quantities of anti-pathogen human plasma and/or immunoglobulin with high avidity antibodies currently requires donations by people that have recovered from and/or were vaccinated for the disease. The number of people required and the time needed to collect sufficient plasma can limit availability of the final product, especially for rare diseases. One novel alternative source of plasma for manufacturing IGIV is transchromosomal (Tc) cattle that produce fully human polyclonal IgG (hIgG) de novo and mount a robust antibody immune response after vaccination.

A human artificial chromosome (HAC) comprising the entire human Ig gene repertoire (human Ig heavy chain and Human kappa light chain) that resides on 2 different human chromosomes (hChr), specifically the IgH locus from hChr14 and the Igk locus from hChr2, was developed. The system maintains the ability to use the genetic information provided by the immunoglobulin gene repertoires for generating the seemingly unlimited diversity of human polyclonal antibodies (hpAbs). For avoiding the possible human-bovine interspecies incompatibility between the human immunoglobulin mu chain protein (hIgM) and bovine transmembrane α and β immunoglobulins (bIg α and bIg β) in the pre-B cell receptor complex, the hIgM constant domain was partially replaced with the counterpart of bovine IgM (bIgM) that is involved in the interaction between bIgM and bIg α /bIg β , to improve the functionality of hIgM in supporting B cell activation and proliferation. Furthermore, the DNA regulatory elements I γ 1 and S γ 1 were bovinized on the HAC to facilitate DNA-protein interactions in the bovine B-cell. This HAC is designated as isKcHAC Δ .

This HAC is placed in the germline of cattle with homozygous triple knockouts (TKO) of the 2 bovine Ig mu heavy-chain loci (bIGHM $^{-/-}$ and bIGHML1 $^{-/-}$) and the lambda light-chain.

Cattle are able to make IgG, but IgM is part of the B-cell receptor. Without IgM, no IgG is produced. Therefore the IgM knockout strategy functionally limits the ability of the cattle to intrinsically produce bovine IgG. There is a phenomenon in the Tc bovine called “trans-class switch” where the HAC IgG is the IgM on the B-cell. Any “trans-bovine” IgG that is produced has a bovine heavy chain and a human variable region. This is removed in the purification method. The purification protocol removes bovine kappa chimeric IgG to very low levels (less than 1%).

Fully human polyclonal IgG (hIgG/hIg κ) can then be produced in high titer in these isKcHAC Δ /TKO Tc cattle, and the cattle produce up to 15 g/L of hIgG in the plasma (similar to humans which have 7-16 g/L IgG).

SAB-301 is an anti-MERS IGIV prepared in this system. Purified Al-Hasa strain MERS-CoV S protein nanoparticles are produced by Novavax, Inc. The S protein was chosen because of its

known immunogenicity and antibodies to this protein have been shown to confer a protective response against viral infection. Just prior to immunization of the Tc bovine, an aliquot of the purified S nanoparticles is thawed and mixed with [REDACTED] and [REDACTED] adjuvants.

Plasma is collected using an automated plasmapheresis system. After collection of sufficient volume, frozen plasma is thawed, pooled, fractionated by caprylic acid and clarified by depth filtration in the presence of filter aid. The clarified sample containing Tc pAbs are further purified by affinity chromatography, first using an anti-human IgG kappa affinity column to capture Tc pAbs and remove residual non-hIgG and bovine plasma proteins and, second, by passing through an anti-bovine IgG heavy chain specific affinity column to further remove residual IgG molecules that contain a bovine heavy chain. The Tc pAb fraction is then subjected to a Q Sepharose chromatography polishing step to further reduce impurities, nanofiltration, final buffer exchange, concentration and sterile filtration.

SAB-301 has been shown to contain high levels of neutralizing antibodies. Preclinical studies suggest SAB-301 is protective for MERS infection. In mice treated with SAB-301 at 24 hours post-infection, and evaluated at 5 days, MERS-CoV titers were below the level of detection in comparison to that observed with untreated control ($p < 0.0001$) or with control hIgG-treated mice ($p < 0.0001$). When SAB-301 was administered 48 hours post-infection, viral titers were reduced $\approx 1,000$ fold by day 5, compared to that observed with untreated control ($p < 0.0001$) or to control hIgG ($p < 0.0001$) (1).

Immunogenicity of low levels of chimeric IgG containing bovine kappa light chain ($< 2.0\%$ of total IgG) and leaked [REDACTED] antibody ligand fragments from the [REDACTED] resin (181.4 ppm) was evaluated in Balb/c mice after three dose administrations by intraperitoneal (IP) injections. This study (Report 68-000148) demonstrated after three administrations of SAB-301 to BALB/c mice at 50 mg/kg and 300 mg/kg, the immunogenicity of SAB-301 in the treated mice was mainly caused by human IgG (2+ to 3+) which was expected. Impurities of SAB-301, bovine kappa light chain had weak and [REDACTED] antibody had minimal to non-detectable immunogenicity in mice. Because of species differences, the occurrence of immunogenicity to bovine kappa light chain and [REDACTED] antibodies in humans treated with SAB-301 is unknown.

SAB-301 has no binding to human or rabbit tissues in standard tissue cross-reactivity studies (Report A398-14). As SAB-301 is a human IgG, there is no ideal animal for pre-clinical toxicity testing as any animal model will see SAB-301 as a foreign protein. Therefore, the safety or toxicity of SAB-301 in animals may not fully predict the safety or toxicity in humans. With acknowledgment of these limitations, however, the animals used were standard preclinical species. In preclinical toxicity studies in a New Zealand White Rabbits model with doses up to 370 mg/kg, no drug-related effects were observed for clinical observations, body weight, hematology and coagulation parameters, and gross necropsy findings (Report M207-15). All animals survived until their scheduled sacrifices. A 2 and 3.9-fold increase in globulin (GLO) was observed in the males treated with SAB-301 at 50 and 370 mg/kg, respectively, compared with the controls on Day 3. The GLO level was also increased, 1.4- and 4.4- fold, respectively in the females in the 200 and 370 mg/kg groups, compared with the controls. Correlatively, the albumin to globulin ratio was decreased, while total protein was increased in these animals. By Day 50, the globulin, albumin to globulin ratio, and total protein returned to normal after 7

weeks recovery period. The increase in globulin level is considered to be test article-related, but could represent an increase due solely to the presence of SAB-301 in the blood. Evaluation on the plasma drug levels, toxicokinetics, and histopathology are in progress.

1.2 Rationale

This study will be the first in human study of Tc Bovine polyclonal human IGIV, and will evaluate the safety and pharmacokinetics of SAB-301. This will both advance treatments for MERS, as well as establish the safety of a platform that could be used to quickly develop therapeutics for other emerging infectious diseases.

2 STUDY OBJECTIVES

2.1 Primary Objective

- To evaluate the safety and tolerability of SAB-301 in healthy adults, following single intravenous administration at escalating dose-levels

2.2 Secondary Objectives

- To evaluate the pharmacokinetics of intravenously administered SAB-301 using MERS neutralization assays in healthy adults, following single intravenous administration at escalating dose-levels
- To evaluate the immunogenicity of SAB-301

3 INVESTIGATIONAL PLAN

3.1 General

Study size: 38 subjects (up to 70 subjects screened to randomize a total of 38 subjects)

Study duration: 1 year

Study duration of individual subjects (not including screening): 90 days

Sex distribution: males and females

Age range: 18 to 60 years

3.2 Study Design

This safety and tolerability study of intravenous (IV) SAB-301 consists of up to 6 single dose-levels or cohorts (cohort 1–6) in a double-blind, randomized, placebo-controlled dose-escalating cohort design. Six cohorts of 3-10 subjects each will be administered a single IV dose of SAB-301 or saline placebo. At very low doses, the concern is primary allergic or T-cell activation/cytokine storm, so small cohort sizes can be utilized. As the target dose is approached, the sample size will increase to increase the likelihood of detecting toxicity events. The cohorts and dose levels are outlined in [Table 1](#).

Table 1: Cohorts and Dose Levels

Cohort	Number of Subjects receiving SAB-301						Number of Subjects receiving Saline Control			
	1.0 mg/kg	2.5 mg/kg	5 mg/kg	10 mg/kg	20 mg/kg	50 mg/kg				
1	2						1			
2		2						1		
3			4						2	
4				4					2	
5					8					2
6						8				2

The administration of the study drug will occur in the day-hospital at the NIH Clinical Center. The number of subjects dosed will follow the limitations below:

- For the first cohort, no more than 1 subject will be dosed on each day.
- For the second cohort, no more than 2 subjects will be dosed on each day.
- For cohort 3-4, no more than 3 subjects will be dosed on each day.
- For cohort 5-6, no more than 3 subjects will be dosed on each day and no more than 6 subjects will be dosed per week.

Beginning with a low single-dose, subjects are randomized to receive either SAB-301 or placebo on Day 0. Subjects are then evaluated on Study Days 1, 3, 7, 21, 42, and 90.

3.3 Definitions for the Purpose of this Study

Definitions for the Purpose of this Study

Enrolled

For the purpose of collecting data and samples and reporting AEs, a subject will be considered enrolled beginning from when the informed consent form is signed until the subject is considered “screen failure”, “discontinued”, or “completed”.

Randomized

Subjects are considered randomized when they meet all of the following criteria:

- Enrolled (as defined above)
- Confirmation that the inclusion and exclusion criteria are met
- Randomization number is assigned

Screen Failures

Subjects are considered screen failures when they meet one or more of the following criteria after signing consent:

- Screening tests reveal that the subject is ineligible.
- Subject withdraws consent before being randomized.

Discontinued

Subjects are considered discontinued when they meet one or more of the following criteria:

- Subject withdraws consent after being randomized and prior to the completion of Day 90 (see Section 4.6).
- Subject is withdrawn after enrollment by Investigator (see Section 4.7) including lost to follow-up.

Completed

Subjects are considered completed when they are followed through Study Day 90 and complete the final study follow-up visit (Study Day 90).

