4.6 Subject Withdrawal

Subjects (or their legal surrogates if subjects become unable to make informed decisions) can terminate study participation at any time without prejudice. If a subject terminates participation before completing the study, the reason for this decision will be recorded in the study record.

Best efforts will be made to follow withdrawn subjects who have received study drug administration for safety. Subjects who withdraw from the study after study drug administration will not be replaced.

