4.7 Discontinuation of Subject by Investigator

The Investigator has the right to withdraw subjects from the study. Subjects may be withdrawn from the study for any of the following reasons:

- The subject is lost to follow-up.
- The Investigator believes that continuation in the study would be detrimental to the subject. In general, subjects withdrawn for AEs will still be followed for safety follow-up if possible.
- If, in the Investigator's best judgment, discontinuation is in the subject's best interest.

The reason for withdrawal from the study is to be recorded in the study record. If a non-serious AE is unresolved at the time of discontinuation, efforts should be made to follow up until the event resolves or stabilizes, the subject is lost to follow-up, or there is some other resolution of the event. The Investigator should make every attempt to follow all SAEs to resolution.

Subjects withdrawn from the study after study drug administration will not be replaced.

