4.9 Emergency Unblinding

If a subject experiences a SAE, and the treating clinician requests unblinding of the study treatment, the Principal Investigator (PI) or designee will be contacted. If the PI or designee is in agreement that unblinding is necessary, the PI or designee will contact the NIH Clinical Center Pharmacy for release of the randomization code for the subject to the treating clinician. The sponsor, Medical Monitor, and DSMB will be informed within one business day that unblinding was necessary. In this case, the subject is still considered enrolled in the study, and the data is still used for analysis.

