12.10.2 Secondary Endpoints

- Pharmacokinetic profile of intravenously administered SAB-301 in healthy adults
- MERS virus neutralization assay
- Frequency and concentrations of antibodies caused by SAB-301, as measured by:
 - Anti-IgG antibodies using rheumatoid factor
 - Anti-SAB-301
 - Anti-Bovine Kappa light chain
 - Anti-██████████ Antibody

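### Section 3.3 ends data, sample and AE collection at discontinuation, in conflict with Sections 4.6, 4.7 and 11.5; new non-serious AEs and later stored-serum results of dosed subjects who leave early are at risk

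*Combined protocol and SAP*

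**What the plan says.** Section 3.3 defines enrolment for a stated purpose and gives it a start: "For the purpose of collecting data and samples and reporting AEs, a subject will be considered enrolled beginning from when the informed consent form". It then gives the end: "is signed until the subject is considered “screen failure”, “discontinued”, or “completed". A subject becomes discontinued in either of two ways: "Subject withdraws consent after being randomized and prior to the completion of Day 90", or "Subject is withdrawn after enrollment by Investigator (see Section 4.7) including lost to follow-up".

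Other sections continue beyond that end point:

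- Section 4.6, after withdrawal by the subject: "Best efforts will be made to follow withdrawn subjects who have received study drug administration for safety".
- Section 4.7, after withdrawal by the Investigator: "In general, subjects withdrawn for AEs will still be followed for safety follow-up if possible". It also calls for follow-up of non-serious AEs that are open at discontinuation, and of SAEs until they resolve.
- Section 11.5 follows AEs to their outcome or to the end of the follow-up period, with no cut at discontinuation. Related SAEs remain reportable after follow-up has ended.

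Sections 4.6 and 4.7 both rule out replacing subjects who leave after dosing. The primary endpoint (12.10.1) is the type and frequency of AEs against placebo. The secondary endpoints (12.10.2) include the PK profile and "Frequency and concentrations of antibodies caused by SAB-301, as measured by" four assays, one of which is rheumatoid factor. Table 3 lists stored serum for PK and immunogenicity in its own block, apart from the safety laboratory tests.

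**The concern.** Read as written, 3.3 stops AE reporting and sampling on the day a dosed subject is discontinued, while 4.6, 4.7 and 11.5 assume that observation goes on. A site could follow either rule. A new non-serious AE found during the retained follow-up would be seen but would have no clear status in the primary endpoint or in the pausing and escalation counts of 12.7 and 12.8. Stored serum is worse placed, because the retained follow-up is for safety only and no section asks for these samples after discontinuation.

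The study gives a single infusion, so leaving the study does not undo the exposure. Later AEs and antibody responses still belong to the dose received. Section 4.7 names withdrawal for AEs, so the loss may be related to how the subject reacted. If those who react are also more likely to form antibodies, the observed antibody frequency would be too low.

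**Working it through.** **1. What each rule covers after discontinuation of a dosed subject**

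| Item | 3.3 | 4.6, 4.7, 11.5 |
|---|---|---|
| AE that led to withdrawal | Inside the window (arose while enrolled) | Followed |
| Non-serious AE still open | Recorded before the window closed | Followed |
| SAE | Window closed for new onset | Followed; if related, reportable even after follow-up ends |
| New non-serious AE | Outside | Observed if follow-up happens; use in the endpoint not stated |
| Rheumatoid factor | Outside | A safety laboratory test, so arguably retained |
| Stored serum, PK and immunogenicity | Outside | Not provided for |

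The exposed items are new non-serious AEs and stored serum. No section defines analysis populations or missing-data handling that would settle either.

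**2. Post-dose samples obtained, by last visit attended (counted from Table 3)**

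Planned post-dose draws: immunogenicity serum 4 (Days 7, 21, 42, 90); rheumatoid factor 5 (Days 3, 7, 21, 42, 90); PK 8 (1 hour, 6 hours, Days 1, 3, 7, 21, 42, 90).

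| Last visit | Immunogenicity serum | Rheumatoid factor | PK |
|---|---|---|---|
| Day 0 | 0/4 | 0/5 | 2/8 |
| Day 1 | 0/4 | 0/5 | 3/8 |
| Day 3 | 0/4 | 1/5 | 4/8 |
| Day 7 | 1/4 | 2/5 | 5/8 |
| Day 21 | 2/4 | 3/5 | 6/8 |
| Day 42 | 3/4 | 4/5 | 7/8 |

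A subject who leaves before the Day 7 visit has no post-dose stored-serum antibody result, but has a rheumatoid factor result if seen on Day 3.

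**3. Share of a cohort**

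Table 1 gives 2 + 2 + 4 + 4 + 8 + 8 = 28 SAB-301 recipients and 1 + 1 + 2 + 2 + 2 + 2 = 10 on saline, 38 in all. One lost recipient is 1/2 = 50%, 1/4 = 25% or 1/8 = 12.5% of the cohort's active subjects.

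**4. Detection probability**

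The plan's own figures come first. P(at least one) = 1 − (1 − p)^N with p = 0.20 gives 0.36 (N = 2), 0.59 (N = 4) and 0.83 (N = 8), as in Section 12.9.1. All 120 cells of Table 5 reproduce to rounding, with a largest difference of 0.005.

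The documents give no withdrawal rate. Assume instead that one or two recipients in a cohort contribute nothing, unrelated to outcome:

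| Planned N | None lost | One lost | Two lost |
|---|---|---|---|
| 8 | 0.83 | 0.79 | 0.74 |
| 4 | 0.59 | 0.49 | 0.36 |
| 2 | 0.36 | 0.20 | no recipients left |

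For AEs this overstates the effect of losing that many subjects, because everything up to discontinuation is recorded. It fits better for an antibody response that appears only in stored serum drawn after the subject has left.

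**The case against.** The strongest reply is that the AE endpoint is largely intact. A reader might infer that subjects withdrawn for a reaction vanish from it. The documents do not say so: the reaction occurs while the subject is enrolled, open AEs and SAEs are still followed, and no section excludes withdrawn subjects from analysis. The reaction also stays in the 12.7 and 12.8 counts. This stands.

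Three other tempting readings also fail:

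- Section 4.9 says of an unblinded subject: "In this case, the subject is still considered enrolled in the study, and the data is still used for analysis". That settles one case. It does not show that the data of discontinued subjects are discarded.
- Stopping an infusion under 5.3 or 12.6 is not discontinuation under 3.3, which needs withdrawn consent or withdrawal by the Investigator. By default that subject stays on the visit schedule.
- Leaving before Day 7 does not mean contributing nothing on immunogenicity, given the Day 3 rheumatoid factor. Samples already drawn remain usable.

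The size of any bias is also open. After a single dose only observation visits remain, and Section 10 pays a $200 bonus for completing them all, so early withdrawal may be rare. One could take the anti-drug antibody rate of the horse antitoxin in Section 8.1.1, 11/271 = 4.1%, and expect 28 × 0.0406 = 1.14 positives, so that losing one erases the signal. But the protocol expects a lower risk with SAB-301. Even at that rate the chance of no positive is (260/271)^28 = 0.31 with nobody lost, and (260/271)^27 = 0.33 with one lost unrelated to antibody status.

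Finally, loss to follow-up and withdrawn consent cannot be cured by wording. That limits the gain but does not answer the conflict for subjects who are withdrawn by the Investigator and remain willing to attend.

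**Conclusion.** The point holds in a limited form. Section 3.3 cannot be applied together with 4.6, 4.7 and 11.5, and no section keeps stored-serum sampling for dosed subjects who leave early. Two things are exposed: new non-serious AEs with onset after discontinuation, and stored-serum antibody and PK results due after it. For a subject who leaves before the Day 7 visit, that is all four post-dose immunogenicity draws.

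One such subject is 12.5% to 50% of a cohort's SAB-301 recipients and is not replaced. Whether estimates are biased, and by how much, depends on how many subjects leave and whether leaving is related to reaction or antibody status. The documents give neither, so no size can be put on it. No stated figure in the plan is wrong.

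This is more than a missing definition, because 3.3 followed literally changes what is collected.

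**What to change.** - **Section 3.3:** for dosed subjects, run AE reporting and data and sample collection to Day 90 or to withdrawal of consent to further contact, whichever comes first, and not to discontinuation. Align 4.6, 4.7 and 11.5 with this.
- **Sections 4.6 and 4.7:** ask withdrawn subjects who still consent to complete the remaining Table 3 visits, including PK and immunogenicity serum.
- **Sections 12.7, 12.8 and 12.10.1:** state that AEs found in that follow-up count in the primary endpoint and in the pausing and escalation reviews.

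The cost is a wording change in these sections and modest effort to retain withdrawn subjects. The visits and samples are already scheduled.
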